The cognitive reorientation intervention we have developed and pilot tested is a simple but potentially powerful strategy to provide structured information in a familiar voice to patients on a regular basis. Because the intervention has a strong nursing care focus, it has the potential to affect delirium in ways that are distinct from but synergistic with medical care, which has focused primarily on pharmacologic management of delirium. The FAVoR intervention we propose in this project holds promise for reducing delirium in critically ill adults, improving sleep in the ICU, and secondarily benefitting cognitive function post-ICU.

We will accomplish the objectives using a prospective, randomized, experimental design to achieve robust and unbiased results. Subjects (n=182) will be randomly assigned within 48 hours of ICU admission and intubation to one of two groups. In the intervention group, scripted audio messages recorded by the patient's family (FAVoR) will be played for the patient at hourly intervals during daytime hours. These messages will be personalized, delivered automatically, and provide information about the ICU environment. Subjects in the control group will not receive recorded audio FAVoR messages. The FAVoR intervention, a standardized protocol developed and tested in preliminary work, will be delivered by audio recording for 5 consecutive days (120 hours), or until ICU discharge if discharge occurs within the first 5 days. The number of episodes of delirium during ICU stay is the primary outcome measure. We will also collect data at 1 month and 6 months following ICU stay for secondary aim 3. A model of the study is presented in Figure 1.

IRB Study Number: 20170771, Version #1.8, Date: 03/10/21, PI: [name]

[figure not shown]
Preliminary Studies

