Primary and Secondary Safety Endpoints. The FAVoR intervention will be interspersed with the care team’s activities, and at no time will the study personnel delay or interfere with critical care procedures; if the needs and activities of providers are such that the study personnel are unable to access the subject to provide audio reorientation, the subject will be withdrawn from the study. At all times, we will place the subject’s need for medical treatment, and avoidance with interference with treatment, foremost.

To reduce skin irritation from applied devices, the Sleep Profiler and ActiWatch will not be placed on skin that is not intact or damaged in any way. The Sleep Profiler and ActiWatch will be removed as soon as data collection is complete (up to 120 hours) and skin assessments will be conducted daily. If the skin shows any signs of irritation, the sleep monitoring devices will be discontinued.

If a 20% or larger fluctuation in vital signs (heart rate and blood pressure) during the recorded message occur, research staff will turn off the recorded message. The clinical nurse assigned to the subject will be immediately notified, and the clinical medical provided will be notified as well. The message will be restarted when the critical care nurse or physician indicates the patient is stable. If the 20% or larger fluctuation in vital signs re-occurs, the intervention will be discontinued and the in-hospital data only up to that point will be included in the study.

Prior to beginning the NIH Toolbox Cognition Battery testing and questionnaires, the subject will be told if they feel excessively frustrated or anxious during the test, they may stop. There is no alternative therapy. However, subjects may elect not to participate and may withdraw from the study at any time without affecting the care they receive.

IRB Study Number: 20170771, Version #1.8, Date: 03/10/21, PI: [name]

9. Procedures Involved

Research Design

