- 1) **Intervention Group:** Subjects in the intervention group will receive personalized digitally recorded reorientation messages administered for up to 2 minutes every hour over an 8-hour daytime period (beginning at 9 am daily) recorded in the voice of a family member. Subjects in the intervention group will continue to receive the intervention for up to a total of 5 days (120 hours), or until ICU discharge if ICU discharge occurs within the first 5 days. Since in the ICU setting delirium has a mean onset of 2.6 days (S.D. +/- 1.7), and a mean duration of 3.4 +/- 1.9 days,⁴⁹ a 5-day period for the study intervention is appropriate and includes the period prior to delirium onset as well as when delirium has been shown to occur most frequently.
- 2) **Control Group:** The control group will consist of usual care, and will not receive audio reorientation messages. Subjects will remain in the study for five days or until ICU discharge if discharged before five days.

Subjects in both groups will be reoriented by care providers as part of usual care practices. Data will be collected from the medical record daily. Both groups (intervention and control) will undergo longitudinal cognitive and patient-reported health status evaluations concurrently with 24-hour sleep profiler-polysomnography and actigraphy at three different points in time. The first time point is inpatient, at least 24 hours after ICU discharge, then outpatient with two home visit data collection events at 1 month and 6 months post hospital discharge.

Description of Intervention. The FAVoR intervention includes a set of 8 recorded messages which were developed in preliminary study 1, and were tested and refined in preliminary study 2. Based on the feasibility data (preliminary study 2) each message is scripted, is no longer than

IRB Study Number: 20170771, Version #1.8, Date: 03/10/21, PI: [name]

2 minutes long, is a personal message using the subject's name, uses simple terms, and is written at a 5th grade reading level. Messages include information about the critical care environment, the visual and auditory stimuli to be expected, and the availability of providers and family. The messages call the patient by name (preferred name as recommended by the patient's family); we believe the use of the patient's name may create greater attention to the message.

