Each message indicates that it is daytime (to provide general time orientation), states that the message is a recorded message, and tells the subject that he/she will hear messages frequently throughout the day to help him/her understand that he/she is in the ICU. Other than the patient's name, the recorded message is generic in nature, and not specific to any one patient condition, procedure, or family situation. Topics for message scripts were developed in response to patients' recollections of the ICU experience.³⁸⁻⁴⁰ The 8 recorded messages will vary randomly in order each day, reducing message repetition, which may eventually annoy or be ignored by the subject.

The messages will be recorded by a family member of the family's choice using a standardized script, in either English or Spanish, based on the family member's decision regarding which language would be most meaningful to the subject. Family members are not human subjects in this project; no data will be collected about the family members. The messages will be digitally recorded using audacity software and stored on the study computer's hard drive as a standard Microsoft wave files. The wave files are loaded onto a small, wireless, digital audio player with a wireless speaker, protected inside a disposable plastic bag, placed near the subject's ear, and set to shuffle play. Shuffle play is a mode of audio playback in which messages are played in a randomized order that is decided upon for all tracks at once and prevents repeated tracks, which makes it distinct from random playback. Shuffle play randomly selects the order of the messages to be played in the patient's room every hour for 8 hours during the daytime, beginning at 9:00 am. The digitally recorded messages will continue at the predetermined daytime intervals each day for a total of 5 days (120 hours), or until ICU discharge if ICU discharge occurs prior to 5 days. All intervention "doses" will be administered during the hours of 9:00 am and 4:00 pm for each of the 5 days, with intervention beginning at the earliest available time following completion of family recording. The research personnel will document the time and number of recordings each day so that a message "dose" can be documented. Research personnel will monitor the subject and the recorded messages regularly to document if the subject was not in the unit (for procedures off the unit etc.) so that those off-unit times can be included in the dose calculation.

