3. SP-PSG (substituted by PROMIS-SD and PROMIS-SRI)
4. NIH Toolbox Cognition Battery (substituted by PROMIS-CF and PROMIS-CFA)

Delirium. The primary outcome measure for this project is delirium free days. We will quantify delirium using the Confusion Assessment Method for the ICU (CAM-ICU).⁴⁵ CAM-ICU scores for each subject will be obtained by study personnel twice daily at 9 am and 4 pm (coinciding with the schedule for initiation and conclusion of messages each day in the FAVoR intervention group, and at identical times for the control group). CAM-ICU scores will also be recorded at the same times for two days following the completion of the intervention period. The Confusion Assessment Method (CAM) will be used during study visits after transfer from the ICU (post ICU, 1 month, and 6 month follow up periods) for comparison.

We will also collect documentation by providers in the medical record of episodes of delirium occurring outside of the CAM-ICU data collection conducted by research personnel. Only days without any instances of delirium will be counted as delirium free days. The CAM-ICU is recognized in the Clinical Practice Guidelines for the Management of Pain, Agitation, and Delirium in Adult Patients in the Intensive Care Unit as a valid, reliable, and feasible tool to detect delirium in ICU patients³ with pooled sensitivity of 75.5% and specificity of 95.8%.⁵⁰

Sleep/Activity. Sleep patterns in the critically ill are highly disorganized, with fragmentation, a predominance of light sleep, and reduction in deep sleep and rapid eye movements.⁸ We will use the FDA approved Sleep Profiler system (Advanced Brain Monitoring, Carlsbad, CA) to obtain continuous polysomnography data (SPPSG). The Sleep Profiler has been successfully utilized in mechanically ventilated and sedated patients and provides three frontopolar electroencephalographic (EEG) signals (AF7/AF8, AF7/Fpz and AF8/Fpz).⁵¹⁻⁵⁴

A wrist actigraph (ActiWatch Spectrum, Philips Respironics, Bend, OR) will be placed on the wrist to measure patient activity and ambient light levels. We have extensive experience with

IRB Study Number: 20170771, Version #1.8, Date: 03/10/21, PI: [name]

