2) minimizing research-associated risk: We anticipate minimal additional physical and psychological risks associated with this study. Reorientation is routinely provided to critically ill patients by bedside nurses as part of clinical care. The intervention will be interspersed with the care team's activities, and at no time will the study personnel delay or interfere with clinical care; if the needs and activities of providers are such that the study personnel are unable to access the subject to provide interventions, the subject will be withdrawn from the study. At all times, we will place the subject's need for medical treatment, and avoidance with interference with treatment, foremost. Because these subjects are receiving clinical care in the hospital, the attending clinical nursing and medical providers will be promptly informed of any adverse effects to the subjects; if an adverse event occurs, necessary interventions will be determined and delivered by the clinical providers.

3) protecting the confidentiality of participant data: In order to reduce risks to privacy of individuals or confidentiality of data, we will not include personally identifiable data in the

IRB Study Number: 20170771, Version #1.8, Date: 03/10/21, PI: [name]

database files. All computers and data files will be password protected, and data will be stored on the University server, with access only to study personnel, under the direct supervision of the PI, [name]. Each subject will be assigned an arbitrary code number to conceal the identity of the research data, and no identifiable private information will be associated with any data files. All data will be collected on laptops in the clinical setting; these laptops will remain in the possession of study personnel at all times (unless locked in a cabinet in the locked research office), and all study-related files will be password protected. At the conclusion of each segment of the subject's participation (ICU, hospital discharge, 1 month post-hospital, 6 months posthospital), that subject's data will be transferred from the laptop computer to a secure, password protected file on the UM server, under the direct supervision of [name], with access limited to study personnel. Study information obtained will be kept strictly confidential, and it will not be possible to identify any participant from the reports that may result from this research.

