- Stop collecting research data.
- Remove all research equipment.
- Mail Thank You card with \$25 gift card to subject’s home address. □ Redact PHI from Enrollment Tracking Log.

In the event the subject (or their LAR) withdraws from the study, we will consider the study complete for the subject and use all information collected up to the point of study withdrawal. The same study completion procedures above will be followed.

13. Risks to Subjects

The risks of participation in the study are minimal. Risks of the intervention may include transient changes in vital signs from stimulation caused by the recorded message. Other risks include skin irritation from the actigraphy watch and sleep profiler-polysomnography, as well as frustration or anxiety with the NIH Toolbox Cognition Battery testing or any of the questionnaires (see Table 1). None of these risks were observed to occur in preliminary study #2.

Following consent and study enrollment, risk of breach of confidentiality is also possible since identifying information will be collected in an electronic enrollment tracking list, on a password

IRB Study Number: 20170771, Version #1.8, Date: 03/10/21, PI: [name]

protected server limited to project director and research assistants, to track the location of subjects as inpatients and contact information for follow up home visits.

There is no alternative therapy. However, subjects may elect not to participate and may withdraw from the study at any time without affecting the care they receive.

Protections Against Risk

The FAVoR intervention will be interspersed with the care team's activities, and at no time will the study personnel delay or interfere with critical care procedures; if the needs and activities of providers are such that the study personnel are unable to access the subject to provide audio reorientation, the subject will be withdrawn from the study. At all times, we will place the subject's need for medical treatment, and avoidance with interference with treatment, foremost.

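### FAVoR subjects whom staff cannot reach to play messages leave the study, while controls face no matching rule, so this post-randomisation loss falls in one arm only.

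*Combined protocol and SAP*

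**What the plan says.** The access rule appears three times.

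- Section 8, Primary and Secondary Safety Endpoints: where providers' work means "the study personnel are unable to access the subject to provide audio reorientation, the subject will be withdrawn from the study".
- Section 11, Data Safety and Monitoring Plan, item b.2: "unable to access the subject to provide interventions, the subject will be withdrawn from the study".
- Section 13, Protections Against Risk: "unable to access the subject to provide audio reorientation, the subject will be withdrawn from the study".

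On the control arm, Section 9 (Group Assignment, item 2) says "Subjects will remain in the study for five days or until ICU discharge if discharged before five days". No section withdraws a control subject whom staff cannot reach.

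Three other provisions bear on the point.

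- Section 9 (Description of Intervention) already keeps a dose record: "The research personnel will document the time and number of recordings each day". Time off the unit enters that record and does not end participation.
- Section 9 also says of both groups: "Data will be collected from the medical record daily". The delirium paragraph adds provider-documented episodes to the research CAM-ICU assessments.
- Section 10 (Data Analysis Plan, Part I) plans multiple imputation under missing at random, with a sensitivity analysis for data not missing at random.

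The primary outcome is named in two ways. Section 4 says "The number of episodes of delirium during ICU stay is the primary outcome measure"; Section 9 says "The primary outcome measure for this project is delirium free days".

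**The concern.** The trigger is a failure to deliver the intervention, and only one arm has an intervention to deliver. Messages are recorded and played after assignment, so every such withdrawal comes after randomisation. The likely cause is intense bedside care, which plausibly goes with severity of illness, and Section 9 itself calls admission severity a well-supported risk factor for delirium. The same busy bedside could therefore remove a FAVoR patient and leave a comparable control in place.

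The rule sets no threshold. Read literally, one blocked message could be enough, and the decision would rest on staff who know the assignment. The study-completion steps in Section 12 include ending research data collection, and nothing exempts access-rule withdrawals from that. On the natural reading, CAM-ICU and the 1- and 6-month visits stop. At stake is whether the arms are observed alike on the primary outcome.

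**Working it through.** **What the plan supplies.** It gives no rate for access withdrawals and no risk for those withdrawn, so there is no figure of its own to reproduce. The documents supply 91 per arm (Section 8), delirium in up to 80% of ventilated patients (Section 4), onset at mean 2.6 days, SD 1.7 (Section 9), W = 0.35 (Section 8), and pilot means of 0.9 and 0.2 delirium days (Section 4, preliminary study 2). The rest is assumed: a fraction *w* of 2-20% of FAVoR withdrawn, and delirium risk *r* among them of 95% when the overall risk *p* is 80%, or 80% when *p* is 50%. There is no true effect.

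**Case 1: withdrawn subjects are dropped.** The FAVoR rate becomes (p − w·r)/(1 − w). For example, with p = 0.80, r = 0.95, w = 0.10: (0.80 − 0.095)/0.90 = 0.7833, a fall of 1.67 points. The false-positive rate is from exact binomial enumeration of the two-sided Pearson 2×2 chi-square test at 0.05, with 91 controls.

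| Withdrawn | FAVoR n | Shift, 80%/95% | False positive | Shift, 50%/80% | False positive |
|---|---|---|---|---|---|
| 0% | 91 | 0 | 4.9% | 0 | 4.5% |
| 2% | 89 | −0.31 | 5.0% | −0.61 | 4.6% |
| 5% | 86 | −0.79 | 5.1% | −1.58 | 5.6% |
| 10% | 82 | −1.67 | 6.0% | −3.33 | 7.2% |
| 20% | 73 | −3.75 | 8.7% | −7.50 | 16.0% |

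Shifts are in percentage points.

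**Case 2: early data are kept and the rest imputed within arm under missing at random.** Assume subjects leave after day 2. With a gamma or lognormal onset time counted from ICU admission, about 56% of onsets fall later, so 44% have been seen. At w = 0.10:

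- p = 0.80, r = 0.95. Seen by day 2: 0.44 × 0.95 = 0.418. Later risk borrowed from retained subjects: 0.56 × 0.7833/(1 − 0.44 × 0.7833) = 0.669. Imputed risk: 0.418 + 0.582 × 0.669 = 0.808, against a true 0.95. Bias in the arm: 0.10 × (0.808 − 0.95) = −1.4 points.
- p = 0.50, r = 0.80. Retained rate 0.4667; borrowed later risk 0.329; imputed risk 0.352 + 0.648 × 0.329 = 0.565. Bias: 0.10 × (0.565 − 0.80) = −2.35 points.

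Imputation reduces the 1.67 and 3.33 point shifts but leaves most of each, because it gives withdrawn subjects the later risk of those who stayed.

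**Case 3: observed delirium-free days are counted without imputation.** A subject leaving after day 2 of 5 loses 3 days. If half would have been delirium-free, the FAVoR mean falls by w × 3 × 0.5: 0.15 days at 10% and 0.30 at 20%. This works against FAVoR. Counting observed episodes over the shorter period works the other way.

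**Scale.** With equal arms in a 2×2 table, W = |p₁ − p₂| / (2√[p̄(1 − p̄)]). Setting W = 0.35 gives a difference of 33.8 points from 80%, or 33.0 from 50%. The pilot difference was 0.9 − 0.2 = 0.7 days.

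**The case against.** The best reply is that the trigger will seldom fire. Messages of at most two minutes play automatically from a small speaker near the patient, and routine non-delivery already goes into the dose record. The rule can be read as a last resort inside a paragraph about not obstructing care. This stands as a reason to expect a low rate, and at 2-5% withdrawn the figures are close to nominal. But the text has no threshold that would make the last-resort reading the operative one.

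Second, the 6-16% false-positive rates cost an analysis the plan does not call for. Section 12 keeps data up to exit for lost eligibility and for withdrawal by the subject or representative, and Section 10 plans imputation and a not-missing-at-random sensitivity analysis. This stands in part: dropping subjects is the unfavourable end. But retention is not stated for access withdrawals, and Section 26 conflicts by having forms destroyed after withdrawal of consent. Case 2 shows that bias persists under missing at random.

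Third, the control sentence describes duration rather than guaranteeing retention, and blocked access would also cost controls in-person CAM-ICU assessments. That is true, but a control would miss an assessment whereas a FAVoR subject would leave the study.

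Finally, a separate FAVoR-only rule cuts off in-hospital data after a repeat 20% vital-sign fluctuation. That is a further problem and does not remove this one.

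**Conclusion.** The concern holds. Followed as written, the rule produces loss after randomisation in one arm, for a reason plausibly tied to acuity, and the plan does not provide for continued outcome collection. The size is uncertain: negligible at 2% withdrawn; at 10-20%, a spurious difference of 1.7 to 7.5 points if withdrawn subjects are dropped, and less if early data are kept and imputed. All of this is small beside the design effect of 33-34 points. The direction depends on which primary outcome is scored and how. The withdrawal rate, excess risk and day of leaving are assumptions. This should be fixed because withdrawal serves no purpose that skipping the message does not, with medium confidence that it matters in practice.

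**What to change.** Keep the priority of clinical care in Sections 8, 11 (item b.2) and 13, and replace the withdrawal clause in each with wording to this effect:

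> Messages that cannot be delivered are skipped and logged in the dose record. The subject stays in the assigned arm. CAM-ICU, chart review, sleep recording where feasible, and the post-ICU, 1-month and 6-month assessments continue on the control-arm schedule, with analysis as randomised.

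This is one amendment in three places, with no new measures, visits or sample size. The cost is a lower average delivered dose in the analysed FAVoR arm, so the estimated effect may be smaller. Because enrolment is under way, subjects already withdrawn under the present wording would remain so; their number and timing should be reported. The vital-sign rule needs its own amendment and could be handled at the same time.

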If a 20% or larger fluctuation in vital signs (heart rate and blood pressure) during the recorded message occur, research staff will turn off the recorded message. The clinical nurse assigned to the subject will be immediately notified, and the clinical medical provided will be notified as well. The message will be restarted when the critical care nurse or physician indicates the patient is stable. If the 20% or larger fluctuation in vital signs re-occurs, the intervention will be discontinued and the in-hospital data only up to that point will be included in the study.

IRB Study Number: 20170771, Version #1.8, Date: 03/10/21, PI: [name]

Prior to beginning the NIH Toolbox Cognition Battery testing and questionnaires, the subject will be told if they feel excessively frustrated or anxious during the test, they may stop. There is no alternative therapy. However, subjects may elect not to participate and may withdraw from the study at any time without affecting the care they receive.

As of March 2020, per the updated guidance regarding research continuity from the University of Miami IRB and research administrations, we are complying with the COVID-19 safety recommendations to protect our subjects, research personnel, students, and faculty members.

14. Potential Benefits to Subjects

Subjects in the intervention group may benefit from this study if delirium is reduced by the FAVoR intervention. The data obtained will provide empirical evidence that will enable us to evaluate the effect of the FAVoR intervention on delirium and holds promise to translate new knowledge into clinical decision-making about the management of delirium in the critically ill to ultimately improve patient outcomes.

15. Vulnerable Populations

Cognitively Impaired Adults

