Subjects will be withdrawn if they appear to be unduly distressed. For example, if a 20% or larger fluctuation in vital signs (heart rate and blood pressure) during the delivery of the recorded message occur, research staff will turn off the recorded message. The clinical nurse assigned to the subject will be immediately notified, and the clinical medical provider will be notified as well. The message will be restarted when the critical care nurse or physician indicates the patient is stable. If the 20% or larger fluctuation in vital signs re-occurs, the intervention will be discontinued and the in-hospital data only up to that point will be included in the study.

Verbal consent to continue participation and for post-hospital follow up will be obtained from the subject as soon as their medical condition permits. We will follow UM IRB, JMH, and UMH policies and procedures. The consenting process for Spanish patients, family members, and/or LAR's will be the same process only with the addition of an individual UMH or JMH Spanish translator or by use of the UMH translation language line phone service, which is available 24 hours a day, 7 days a week.

Pregnant Women

This minimal risk study carries no added risk to pregnant women and the well-being of their unborn child.

16. Sharing of Results with Subjects

Individual subject results will not be shared with subjects or others (i.e., health care providers) during the study. De-identified study group results will be made available through publications and summarized on clinicaltrials.gov.

17. Setting

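### A data cut-off that only the FAVoR arm can trigger removes primary-outcome ICU days, and the missing-data plan is not tied to those days

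*Combined protocol and SAP*

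**What the plan says.** The rule appears in Section 8 (Primary and Secondary Safety Endpoints), Section 13 (Protections Against Risk), Section 15 (Cognitively Impaired Adults) and twice in Section 26 (Cognitively Impaired Adults; Adults Unable to Consent). After a second fluctuation during a message, "the intervention will be discontinued and the in-hospital data only up to that point will be included in the study". In Sections 8 and 13 the event ends the messages. In Sections 15 and 26 it is given as an example under the statement "Subjects will be withdrawn if they appear to be unduly distressed".

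Section 9 (Group Assignment) says: "The control group will consist of usual care, and will not receive audio reorientation messages". For both arms, "Data will be collected from the medical record daily". Section 9 (Delirium) schedules CAM-ICU twice a day, at the same times in controls, and adds: "CAM-ICU scores will also be recorded at the same times for two days following the completion of the intervention period". Table 1 agrees, with ICU days 1-5 and 6-7.

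The primary outcome is given in two ways. Section 4 says "The number of episodes of delirium during ICU stay is the primary outcome measure". Section 9 names delirium free days and says "Only days without any instances of delirium will be counted as delirium free days".

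Section 10 (Data Analysis Plan, Part I) plans multiple imputation under missing at random for missing primary-outcome values. It adds a sensitivity analysis for data not missing at random, using an intent-to-treat method for longitudinal studies with dropouts. Neither mentions the days lost under this rule.

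**The concern.** The trigger needs a message to be playing, so a control patient can never meet it. Death, discharge and withdrawal of consent can shorten observation in either arm, but this route cannot, and randomisation does not balance it. The patient may still be in the ICU with delirium assessments due, and those assessments do not depend on messages.

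A patient cut on day 3 still has a number of episodes or of delirium free days. An analyst could enter that number as complete, and the imputation step would then never be reached. Some FAVoR patients would be observed for less time than controls for a reason tied to treatment, and the direction of the bias would depend on which primary outcome is used.

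**Working it through.** **1. Which arm can lose days.** The trigger is a fluctuation during a message (Section 8). Messages go to FAVoR patients only (Section 9). The cut is therefore confined to one arm.

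**2. Whether the loss is necessary.** Controls have CAM-ICU and chart review without messages, and CAM-ICU continues for two days after messages end. Stopping messages does not by itself prevent assessment.

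**3. How often.** The documents give no rate. Section 13 reports that none of the listed risks occurred in preliminary study 2, in which 20 patients heard messages (10 family voice, 10 non-family voice) over three days.
- One-sided 95% upper bound for 0 of 20: 1 - 0.05^(1/20) = 0.139.
- Family-voice patients only, 0 of 10: 1 - 0.05^(1/10) = 0.259.

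The pilot's messages ran for three days against up to five here, so neither figure is a reliable ceiling or an expected rate.

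**4. Size if the days are left out.** Simulation with no true effect. Bias is measured against the same patients' full data.
- From Section 9: delirium onset mean 2.6 days (SD 1.7) and duration mean 3.4 days (SD 1.9), drawn as gamma.
- Ever delirious: 60% (assumed) or 80% (upper figure in Section 4).
- Assumed: 10% of FAVoR patients cut, after day 1 to 4 with equal chance; delirious patients equally or twice as likely to be cut.

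| All patients stay | Any delirium, FAVoR minus control | Delirium free days, FAVoR minus control |
|---|---|---|
| 7 days | -2.7 to -4.1 points | -0.21 to -0.29 |
| 5 days | -2.3 to -3.5 points | -0.10 to -0.15 |

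Ranges span the four combinations of delirium rate and cut risk. The bias is roughly proportional to the cut rate. With 7-day stays, a 5% cut gives 1.4 to 2.1 points and 0.10 to 0.15 days; a 14% cut gives 3.8 to 5.8 points and 0.30 to 0.40 days.

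**5. Size if the days are imputed.** At a 10% cut, a simple within-arm imputation matched on delirium before the cut left about zero bias when cuts were unrelated to delirium. When delirious patients were cut twice as often, it left at most 1.0 point and 0.03 days. This is a stand-in for the planned multiple imputation.

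**6. Scale.** The planned effect is W = 0.35 (Section 8). In an equal-arm 2x2 table the difference in proportions is 2 x W x sqrt(p(1-p)), where p is the pooled proportion.
- p = 0.5: 2 x 0.35 x 0.5 = 0.35.
- p = 0.8: 2 x 0.35 x 0.4 = 0.28.

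The any-delirium bias at a 10% cut is thus between 2.3/35 = 7% and 4.1/28 = 15% of the planned effect.

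**7. Days and checks lost at a 10% cut.** 10% of 91 is 9.1 patients, and the mean cut day is 2.5.
- 7-day stays: 9.1 x 4.5 = 41 days, or 82 twice-daily checks. The schedule holds 182 x 14 = 2,548, so this is 3.2%.
- 5-day stays: 9.1 x 2.5 = about 23 days.

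**The case against.** The strongest reply is that Section 10 already covers this. It imputes missing primary-outcome values and names an intent-to-treat method for dropouts, and a patient whose in-hospital data end early is an ordinary case for it. On that reading little bias remains (step 5). This stands, and it limits the point to a missing link. A reader might infer that the plan has no handling for such losses; the text does not support that. What remains is that nothing identifies a shortened count as missing.

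A reader might also infer that days after the cut would be scored as delirium free and so create a false benefit, because no delirium is recorded on them. The clause includes "the in-hospital data only up to that point will be included in the study", so later days cannot enter as delirium free without setting that clause aside.

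A third inference is that withdrawal because staff cannot reach the patient causes the same one-sided loss. The text does not state what data are then lost, and blocked access could prevent bedside assessment in either arm.

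Rarity is a fair objection too. The 10% rate is an assumption, and the true rate could be near zero. Finally, for delirium free days the uncounted-day bias works against FAVoR. A false benefit needs the episode count, or an any-delirium split that the documents do not define.

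**Conclusion.** The concern holds in limited form, as a minor to moderate point. Followed as written, the rule shortens primary-outcome observation in the FAVoR arm only, and the existing missing-data plan is not tied to the days removed.

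With the days left uncounted, a 10% cut and no true effect, any delirium is lower in FAVoR by 2.7 to 4.1 points (7-day stays) or 2.3 to 3.5 points (5-day stays). Delirium free days are lower by 0.21 to 0.29 or 0.10 to 0.15. These sizes rest on the assumed cut rate, cut timing, share ever delirious and length of stay. The one-arm mechanism rests on the text alone. If Section 10's imputation is applied to these days, little bias remains.

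**What to change.** Leave unchanged when messages stop and when distressed subjects are withdrawn.

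1. **Reconcile the passages.** Say whether the repeated fluctuation ends messages only (Sections 8 and 13) or participation (Sections 15 and 26). Align this with Section 12, which stops data collection and uses data to that point after withdrawal or study completion, and with the opening of Section 26, under which data forms are destroyed when the subject or representative stops.

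2. **Replace the data clause** for patients whose messages stop but who remain in the study:

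> Scheduled CAM-ICU, chart review and follow-up continue where consent and the patient's condition allow, and the patient is analysed in the arm assigned.

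3. **Add to Section 10, Part I:**

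> ICU days not assessed after messages stop, after withdrawal or after study completion while the patient is alive in the ICU are treated as missing, not as delirium free or uncounted. They are imputed using earlier CAM-ICU results and covered by the not-missing-at-random sensitivity analysis. Numbers of patients and days are reported by arm.

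**Cost.** One amendment and a few bedside checks by existing staff: about 82 of 2,548 at a 10% cut with 7-day stays. Because this is already Version 1.8 (March 2021), two data rules would exist within one trial, and CAM-ICU cannot be recovered for patients already cut. The Section 10 addition involves no bedside work.
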